DISSEMINATION AND PROJECTED OUTPUTS
OUTPUTS
DISSEMINATION
MANAGEMENT PLAN
REGULAR COMMUNICATION
APPROVAL BY ETHICS COMMITTEES
PATIENT AND PUBLIC INVOLVEMENT26
REFERENCES
APPENDIX 1

SUMMARY OF RESEARCH

AIM/S

Although osteoporosis and fragility fractures are common amongst CKD patients, the effectiveness and safety of first-line anti-fracture therapies (bisphosphonates) for this population are still unclear. We therefore aim to study the association between oral bisphosphonate (OB) use in stage ≥3B CKD patients and the following outcomes: CKD progression (stage worsening or entering renal replacement therapy or transplant) (WP1), clinical fracture/s (WP2), adverse events (hypocalcaemia or hypophosphatemia, upper gastro-intestinal events, and acute kidney injury) (WP3), and axial bone mineral density (WP4).

METHODS

Data sources: the primary data source for WP1-3 of our study will be the Clinical Practice Research Datalink (CPRD), linked to the Hospital Episodes Statistics (HES). Data from the Danish Odense University Hospital Database (OUHD) will be used for WP4.

Study participants: all patients registered in CPRD or in OUHD, aged \geq 40 years, with an eGFR<45, and with \geq 1 years of follow-up data available will be included. Users of bisphosphonates in the year before eGFR testing, as well as CPRD participants with no possible linkage to HES data will be excluded.

Exposure: Users of oral bisphosphonates will be identified from primary care prescriptions (CPRD) or pharmacy dispensations (OUHD).

Outcomes: WP1: CKD progression will be defined as stage worsening (according to eGFR as recorded in CPRD) or initiation of renal replacement therapy/transplant (HES).

Study outcomes for WP2-3 will be ascertained using previously validated lists of READ/OXMIS (CPRD) (1-3) or ICD-10/OPCS (HES) (4) codes. The main study outcomes will be: all clinical fractures excluding the skull/face and digits, which are not considered to be osteoporotic (WP2), and adverse events (hypocalcaemia/hypophosphatemia requiring hospital admission, upper gastro-intestinal events, and hospitalization for acute kidney injury) for WP3. WP4: annualized hip bone mineral density percentage change, as measured using DXA scan, will be measured.

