The current proposal will assess the risks and benefits of the use of oral bisphosphonates to prevent fragility fractures amongst patients with stage \geq 3B CKD. Oral bisphosphonates are the first line therapies for the primary and secondary prevention of osteoporotic fractures, as recognized by NICE guidelines (TA 160 and 161), but they are contraindicated in patients with eGFR<30-35. The drugs assessed will be the currently recommended ones: oral alendronate, risedronate, and ibandronate.

Use of oral bisphosphonates will be identified using pre-specified lists of the British National Formulary (BNF) within CPRD, and Anatomic Therapeutic Classification (ATC) codes for OUHD (Appendix 1).

There is no approved alternative bone medication for patients with severe CKD, and therefore oral bisphosphonate users will be compared to those not on anti-osteoporosis therapy (i.e. drug non-users).

EXPOSURE PERIODS

As the data sources include information on drug prescribing (CPRD) or dispensing (OUHD) as opposed to drug consumption, the prescription duration may not reflect the true number of days over which a prescription was used. As a result, assumptions will be made to account for non-adherence (or non-compliance) in order to define periods of continuous exposure.

We will assume that any overlap between two prescriptions of the same bisphosphonate represent early collection of a repeat prescription. Hence, any overlapping days between two prescriptions of the same drug will be added to the end of the period covered by the two prescriptions. In order to define periods of continuous use of study drugs, any two prescriptions of the same drug will be concatenated if the gap between the end of the first of the two prescriptions and the start of the second of the two prescriptions was less than 30 days apart.

DESIGN AND THEORETICAL/CONCEPTUAL FRAMEWORK

CONCEPTUAL FRAMEWORK

An observational cohort study using routinely collected data will be performed to evaluate the potential risks (CKD progression, hypocalcaemia/hypo-phosphatemia, and a number of adverse events) and benefits (bone density improvement, and fracture protection) observed amongst patients with stage ≥3B CKD in actual 'real life' NHS practice.

STUDY DESIGN

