The chosen study design is a propensity score-matched retrospective cohort study. This is one of the best pharmaco-epidemiological designs available for the assessment of intended (benefits) and unintended (risks) effects of drugs in observational data. Propensity score-matching will therefore be used to match each eligible bisphosphonate user to 5 non-users, producing matched comparable (in terms of observed baseline characteristics) cohorts.

TARGET POPULATION

The target population of this study will be patients with an eGFR<45 (based on serum creatinine) aged 40 years or older at the age of biochemistry testing.

EXCLUSION CRITERIA

From the population described above, we will exclude those with any of the following exclusion criteria:

- Less than 1 year of follow-up data available within the data source/s.
- CPRD participants with no possible linkage to HES.
- Use of anti-osteoporosis medication/s in the previous year (except calcium and/or vitamin D supplements).
- Use of any (except calcium and/or vitamin D supplements) other anti-osteoporosis medication/s (other than bisphosphonates).

SETTING/CONTEXT

Setting: The proposed study will obtain data from both primary (CPRD) and secondary (HES) care.

Study period: Currently used oral bisphosphonates (alendronate, risedronate and ibandronate) were approved and launched to the market in 1996 onwards. Our study period will therefore cover from 1996 to the latest data extraction for the identified data sources, likely 31/12/2014.

Follow-up: Data from randomized placebo-controlled trials have shown that bisphosphonates are effective to reduce fracture risk only after at least 6 months of continuous use (27). That is not the case though for adverse events, which can be observed immediately after bisphosphonate therapy initiation (14, 17, 28). Therefore, different follow-up windows will be established, as follows:

- Safety outcomes (WP1 and WP3): Patients will be followed from the latest of the following dates
- a) Start of study period
- b) One year of valid data in database
- c) Date of incident prescription of bisphosphonate (after one year of non-use)

until the earliest date of:

- a) The end of enrolment in the database (due to moving out or death)
- b) Date of last data update in the database
- c) Stopping of treatment +30 days (no repeat prescription within 1 month)
- d) Switch of treatment to other (non-bisphosphonate) osteoporosis medication

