- e) Outcome of interest (different date for each study outcome)
- Effectiveness outcomes (WP2 and WP4): Patients will be followed from the latest of the following dates
- a) Start of study period
- b) One year of valid data in database
- c) Date of continued prescriptions of an oral bisphosphonate for 6 months after the date of therapy initiation

until the earliest date of:

- a) The end of enrolment in the database (due to moving out or death)
- b) Date of last data update in the database
- c) Stopping of treatment +180 days (no repeat prescription within 6 months)
- d) Switch of treatment to other osteoporosis medication, with no repeat prescription of oral bisphosphonates within the next 6 months
- e) Incident recorded fracture (WP2) or last BMD measurement available (WP4)

SAMPLING

One of the advantages of routinely collected datasets is that the contained information is readily available, not needing active recruitment. Therefore, all patients eligible (see target population and exclusion criteria above) registered in the chosen data sources will be included.

Sample size/power: According to feasibility counts provided by CPRD, the number of eligible patients (with an eGFR<45 and possible to link to HES) would be of 204,528 subjects, and 34,127 (16.7%) of these received oral bisphosphonate prescriptions. These numbers would provide statistical power to reliably answer each of the study aims, as it can be seen below:

Work-package 1: In a survival analysis (log-rank 2-sided test), accepting 5% type I error and 20% attrition from propensity score matching and loss to follow-up in 2 years, and assuming CKD stage progression rates of 12/100 person-years (29), the available number of participants would provide 90% power to detect an excess risk of CKD progression of 10% or more (HR \geq 1.10) associated with oral bisphosphonate use.

Work-package 2: In a log-rank (2-sided) test, and accepting 5% type I error and 20% drop-out, with 2 years of follow-up and an expected fracture rate of 103/10,000 person-years in CPRD data (30), the available sample size would provide 90% power to detect a fracture reduction of at least 15% (HR≤0.85) amongst oral bisphosphonate users (compared to non-users).

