Immortal time bias and time-varying exposure: Immortal time bias (ITB) is a common issue in pharmaco-epidemiology. In brief, ITB appears when in a study the event of interest cannot occur for a certain time span due to study design and/or data analysis methods used (26). In cohort studies, immortal time typically arises when the definition of drug use involves a delay or wait period during which follow-up time is accrued—for example, waiting for a prescription or drug dispensation after discharge from hospital when the discharge date represents the start of follow-up (38).

A number of methods are available to avoid ITB. We will, in our study, use time-varying exposures, where in a survival analysis the time previous to index date for drug users (i.e. the time before first prescription of oral bisphosphonates) is reclassified as drug non-user personyears. We have extensive expertise using this method (39-41), which has been shown to be the most efficient to avoid ITB in pharmaco-epidemiological studies (42).

Hazard ratios: We will use proportional hazards Cox regression modelling to estimate the Hazard Ratio (HR) and 95% Confidence Intervals for each of the outcomes of interest according to bisphosphonate use. To account for the matched cohort approach proposed, we will use Cox regression stratified by matched sets.

The proportional hazards assumption will be checked using clog log plots. Alternative models, e.g. parametric survival models and weighted Cox regression(43) will be considered. The final decision of the alternative modelling techniques will depend on the availability of a suitable function to describe the hazards distribution.

If mortality rates are different amongst bisphosphonate users and matched non-users, Fine and Gray survival analyses (44) will be used instead, to account for a competing risk with death.

Failing to do so would results in a biased estimation of the excess/reduced risk of the events of interest amongst bisphosphonate users (45).

Beta coefficients: Longitudinal analysis will be used to study the association between bisphosphonate use and annualized changes of both eGFR (secondary outcome in WP1) while linear regression modelling will be used to study the association between bisphosphonate use and changes of BMD between two observed time points (WP4). Beta coefficient and 95% confidence intervals will be reported for the effect of bisphosphonate use on both outcomes.

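### A one-year look-back lets people restarting a bisphosphonate count as incident users and former users serve as non-users, which may bias the WP3 harm estimates towards no effect; the index date needs one definition and a check in people with no earlier recorded use

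*Protocol*

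**What the plan says.** Four parts of the protocol bear on who is a new user and who is a non-user.

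- **Follow-up (Setting/Context).** For the safety outcomes (WP1, CKD progression; WP3, adverse events), one of the start dates is the "Date of incident prescription of bisphosphonate (after one year of non-use". For the effectiveness outcomes (WP2, fractures; WP4, bone density) it is the "Date of continued prescriptions of an oral bisphosphonate for 6 months after the date of therapy initiation". Both lists ask for only "One year of valid data in database".
- **Exclusion criteria.** Patients are removed for "Use of anti-osteoporosis medication/s in the previous year (except calcium and/or vitamin D supplements". The further exclusion, for other anti-osteoporosis drugs, exempts bisphosphonates. The Summary of Research gives the year a different anchor, removing "Users of bisphosphonates in the year before eGFR testing".
- **Health technologies being assessed.** On the comparator: "oral bisphosphonate users will be compared to those not on anti-osteoporosis therapy (i.e. drug non-users".
- **Data analysis, immortal time bias.** For drug users, "the time before first prescription of oral bisphosphonates) is reclassified as drug non-user personyears".

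The Sensitivity analyses section covers interactions, a gradient by medication possession ratio and laboratory-defined calcium and phosphate events. It contains nothing on earlier bisphosphonate use.

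**The concern.** With a one-year look-back, someone who took a bisphosphonate, stopped for more than a year and restarted meets the definition of an incident user. Someone who stopped more than a year ago and did not restart is not barred from the comparator. How use before that year is handled is not stated for either group.

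This matters most for WP3. The Follow-up section says adverse events can be seen as soon as treatment starts. People who had an early event and gave the drug up for good will be under-represented among restarters, so restarters plausibly carry less excess risk than first-time users. Mixing them in would move the hazard ratio towards 1. Under Target audience, the protocol says its results may change current restrictions on these drugs. A bias towards no harm is the less comfortable direction in such a study.

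The wording also leaves room for two different cohorts, because the index date and the anchor of the year are each described in more than one way.

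**Working it through.** **1. The definitions side by side.** Two illustrative patients show where they part.

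- Patient A took a bisphosphonate and stopped five years before the low eGFR, then restarted one year after it. By the Follow-up rule the index date is the restart. Read literally, the immortal-time section's first prescription is the one from years earlier, before cohort entry. Read as the first qualifying prescription, it is the restart.
- Patient B had a last prescription six months before the eGFR test and restarted 18 months after it, so was 24 months off drug. The Summary excludes this patient (use in the year before testing). The Follow-up rule admits the patient as incident.

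For someone whose first ever prescription follows cohort entry, the rules agree. The difference is confined to use before entry.

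**2. Reproducing the plan's own figure.** Table 1 gives 21,578 users for HR 1.2, 2% two-year incidence, 90% power and 1:5 matching. Taking two proportions with p0 = 0.02 and p1 = 1 − 0.98^1.2 = 0.02395, two-sided alpha 0.05, gives 17,125 users. Allowing for 20% dropout, 17,125 / 0.8 = 21,407, within 0.8% of the stated figure. The power section is not in error on this point.

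**3. Effect of restarters on WP3.** The protocol gives no share of restarters, so a share f of 10-30% is assumed, with no excess risk among them:

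observed HR = 1 + 0.20 × (1 − f)

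This gives 1.18 at f = 0.10, 1.16 at f = 0.20 and 1.14 at f = 0.30.

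**4. What that does to power.** By Schoenfeld, with U users, five non-users each and incidence p0:

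D = U × (p1 + 5 × p0), where p1 = 1 − (1 − p0)^HR

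power = Φ(√(D × 1/6 × 5/6) × |ln HR| − 1.96)

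U = 34,127 × 0.8 = 27,302. At 2% and HR 1.20, D = 27,302 × (0.02395 + 0.10) = 3,384, and the power is Φ(√(3,384 × 0.1389) × 0.1823 − 1.96) = Φ(1.99) = 98%.

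The fair comparison is not with that 98%, because restricting to first-time users also removes the restarters. The right-hand columns therefore use U × (1 − f) users at HR 1.20.

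| Restarters f (assumed) | Observed HR, mixed | Power mixed, 2% | Power restricted, 2% | Power mixed, 1.6% | Power restricted, 1.6% |
|---|---|---|---|---|---|
| 10% | 1.18 | 95% | 96% | 89% | 92% |
| 20% | 1.16 | 89% | 94% | 82% | 89% |
| 30% | 1.14 | 81% | 91% | 72% | 84% |

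The 2% incidence is the WP3 planning value; 1.6% is the protocol's figure for serious upper gastro-intestinal events. For all such events the protocol gives 11%, and there power stays above 99% even at HR 1.14.

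**5. WP1 and WP2.** For WP1, with 12/100 person-years over two years, the most adverse mixture tried (30% of users with no effect, 10% of non-users with the full effect) takes HR 1.10 to 1.059 and leaves 98% power.

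For WP2, the rate of 103/10,000 person-years over two years and HR 0.85 gives 93% power, against 90% stated. If 10% of non-users were former users keeping the whole protection, the observed HR would be 0.85 / (1 − 0.15 × 0.10) = 0.863 and power 88%. The reverse can also happen: if 20% of users were restarters with a larger cumulative benefit (assumed HR 0.75), the observed HR would be 0.8 × 0.85 + 0.2 × 0.75 = 0.83.

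**The case against.** A one-year washout is a stated design choice, and it appears both in the exclusions and in the start of safety follow-up. The immortal-time section explains how person-time before a user's index date is classified; it does not set out to redefine incident use, so its first prescription can be read as the first one that qualifies. With only one year of data required, a rule based on all available records would give each patient a different look-back and could not guarantee a true first use. Every share above is assumed, and zero excess risk in restarters is the extreme case: the protocol says events can occur immediately, not that risk is confined to that period.

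Most of this stands. It makes the index date an ambiguity rather than a plain contradiction, and it leaves the size of any bias open. It does not tell the reader how earlier use is handled, nor does it reconcile the two anchors of the year.

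A reader might infer that harm and benefit are both diluted. The documents do not support that. Former users among the comparators weaken WP2 only if protection lasts beyond a year off drug, whereas follow-up is extended for just 30 days (safety) or 180 days (effectiveness) after stopping. Restarters' earlier exposure could leave the benefit unchanged or larger. A reader might also infer a fall in power from 98% or 94%, but those baselines include the users whom the restriction would remove.

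**Conclusion.** The concern holds in a limited form. The protocol admits restarters as incident users and does not bar former users from the comparator. It also describes the index date and the look-back year in ways that could yield different cohorts. A bias of WP3 towards no harm is plausible: an observed HR of 1.18-1.14 for a true 1.20, if 10-30% of users are restarters with no excess risk. Against a restricted analysis, the corresponding loss of power is about 2 to 10 points at 2% incidence and 3 to 13 points at 1.6%. These figures rest wholly on the assumed share and on zero excess risk in restarters. WP1 power is barely affected, and neither the presence nor the direction of a bias in WP2 is established. No power figure in the protocol is shown to be wrong. This is a worthwhile, inexpensive improvement rather than a fault that undermines the study.

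**What to change.** - Use one index-date definition in the Summary, the Exclusion criteria, the Follow-up section and the immortal-time section. State whether first means first recorded or first after a year of non-use, and which date the look-back year is counted from.
- State how bisphosphonate use before that year is handled for users and for comparators.
- Add an analysis limited to users whose index prescription is their first recorded oral bisphosphonate, and to comparators with no bisphosphonate recorded before index. Report it beside the one-year-washout analysis, with the number of people removed from each group, which would also supply the missing share of earlier users.

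The cost is a change to the cohort query on data already held and a repeat of the matching. User numbers fall in proportion to the share of restarters (by 10-30% under the assumption above). Look-back length will differ between patients, and use before a patient's records begin stays unseen, so the restriction reduces the problem without removing it.

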While there are effective therapies to reduce the risk of fracture, the use of first line antiosteoporosis therapies (i.e. oral bisphosphonates) is restricted in patients with CKD for two main reasons: 1.there are safety concerns related to the risk of bisphosphonates worsening kidney function and other adverse events which are already increased in patients with CKD such as severe hypocalcaemia or hypophos-phaetemia (which has been observed in about 8% of cancer patients treated with powerful intravenous bisphosphonates (13)), upper gastrointestinal events, or acute kidney injury; and 2. given the biological mechanism of how CKD weakens bone differs from osteoporosis, it is far from established that bisphosphonates will have a similar beneficial effect in reducing fracture rates. Efficacy data for bisphosphonates is scarce in CKD, as the numbers of patients with moderate or severe CKD recruited for the pivotal trials were low, with only 301 patients with an eGFR<30 being recruited in the risedronate arm from a total of 9 randomized controlled trials (14). Importantly, participants in these trials with CKD are likely to be healthier and have fewer co-morbidities compared with patients with CKD in the real life setting as we have previously shown [[name] et al. "RCT Participants and Real Life Drug Users: A Population-Based Cohort Study". Poster presentation at ISPE 2014 Conference, Taiwan]. Another concern is that about 40%-45% of patients with end-stage renal disease (15, 16), and an unknown proportion of those with stage 4 CKD, may suffer adynamic bone disease where there is a marked reduction in activity of the cells in bone. Given the mechanism of action of bisphosphonates is to further reduce activity of bone cells (osteoclasts), there remains a concern that use of anti-resorptive medications such as bisphosphonates in this setting would increase and not decrease the risk of fracture.

Given all this, and despite good safety data from randomized trials for both risedronate (14) and alendronate (17), NICE guidelines (TA160 and 161) do not support the use of bisphosphonates in patients with eGFR<35, and oral bisphosphonates are not recommended with eGFR<35 (alendronate (18)), or eGFR<30 (ibandronate (19) and risedronate (20)), mainly due to a lack of experience rather than evidence demonstrating worse outcomes (see Fosamax SPC EMC). This leaves this patient group with a very high fracture risk effectively untreatable.

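### WP1 ends users' follow-up 30 days after stopping, a decision that falling eGFR can itself prompt, so the hazard ratio for CKD progression can be biased towards no harm by an unknown amount

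*Protocol*

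**What the plan says.** Under Setting/Context, Follow-up, WP1 and WP3 share one safety window. End criterion c) reads "Stopping of treatment +30 days (no repeat prescription within 1 month". The effectiveness outcomes (WP2 and WP4) have a longer one: "Stopping of treatment +180 days (no repeat prescription within 6 months". The reason given for separate windows is about when effects begin: "That is not the case though for adverse events, which can be observed immediately after bisphosphonate therapy initiation". Nothing is said about why a short tail suits CKD progression.

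The Summary of Research gives the WP1 outcome: "CKD progression will be defined as stage worsening (according to eGFR as recorded in CPRD", or the start of renal replacement therapy or transplant. Under Target population: "The target population of this study will be patients with an eGFR<45 (based on serum creatinine".

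On limits to use, Background and Rationale states that "oral bisphosphonates are not recommended with eGFR<35 (alendronate (18)), or eGFR<30 (ibandronate (19) and risedronate (20". Health Technologies Being Assessed repeats that "they are contraindicated in patients with eGFR<30-35".

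Under Data Analysis, the hazard ratio comes from a Cox model stratified by matched sets. Annualized eGFR change is a secondary WP1 outcome, analysed longitudinally.

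**The concern.** A Cox model takes censoring to be unrelated to the event risk of those censored. Here the reason for censoring and the event share one variable. A stage 3B user whose eGFR drifts into the low 30s has a stated reason to be stopped, leaves follow-up a month later, and may have no further eGFR test in that month. A non-user with the same decline stays under observation and is counted when the next test shows stage worsening. The users still at risk are then a selected group with better renal function, and their hazard looks too low.

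Propensity matching balances baseline only, whereas this selection arises afterwards. WP1 is meant to inform regulators about renal safety, so a bias towards no excess progression is the costly direction.

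**Working it through.** **1. The plan's own WP1 figure.** Inputs from Sampling: 34,127 users, 204,528 − 34,127 = 170,401 non-users, 12 events/100 person-years, 2 years, HR 1.10, two-sided 5%, 90% power. The attrition input is "accepting 5% type I error and 20% attrition from propensity score matching and loss to follow-up in 2 years". (The Summary of Research prints a different user count and target HR; the Sampling section is used here.)

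- Events needed (Schoenfeld): (1.960 + 1.282)² / [(1/6)(5/6)(ln 1.10)²] ≈ 8,329.
- Events expected: 0.8 × [34,127 × (1 − e^−0.264) + 170,401 × (1 − e^−0.24)] ≈ 35,422.

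Power is above 99.9%, so the stated 90% is a conservative floor. It is not the problem. The HR detectable with 90% power is exp(3.242 / √(0.1389 × 35,422)) ≈ 1.05. The standard error of log HR is 1/√(0.1389 × 35,422) ≈ 0.014, a 95% half-width of about 3%. A bias of 1-2% would lie within sampling error; one of 8-9% would not.

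**2. Bias needed to cancel an effect.** A true HR of 1.10 is seen as 1.00 if the users' hazard is understated by 1 − 1/1.10 = 9.1%. For HR 1.20 it is 1 − 1/1.20 = 16.7%.

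**3. Who is affected.** Taking 30 as the stage 3B/4 boundary (an assumption; the protocol does not print it):

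- Alendronate, stage 3B: the stated limit (35) lies above the boundary, so a stop at 30-35 precedes the event. Exposed.
- Ibandronate or risedronate, stage 3B: the stated limit (30) is the boundary, so the reading that prompts the stop is already the event. Exposed only if prescribers stop in anticipation.
- Entry at stage 4 or worse: no limit is stated at the next boundary.

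The drug mix is not given.

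**4. Simulation, no drug effect.** Assumptions: baseline eGFR uniform 30-45, slope −1 (SD 1.5) per year, four six-monthly tests with 5% noise, event = test below 30, unrelated stopping 15%/year, users reading 30-35 stopped with probability q per test and censored 30 days later. The control rate is 12.3/100 person-years, against the protocol's 12.

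| q | everyone reading 30-35 exposed | only those who fall from ≥35 exposed |
|---|---|---|
| 5% | 0.95-0.96 | about 0.99-1.00 |
| 10% | 0.91-0.92 | about 0.99 |
| 25% | 0.81 | about 0.98-0.99 |
| 50% | 0.65 | about 0.98 |

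Following users past stopping gives about 1.00. The columns differ because about 88% of events come from patients starting below 35.

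**5. A second model.** Patients move from above 35, to 30-35, to below 30. One third start in the 30-35 band and are not subject to threshold stopping. Those crossing into it stop with probability p. Background stopping is 0.3/year.

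| p | true HR 1.00 seen as | full-follow-up HR 1.10-1.13 seen as |
|---|---|---|
| 0.25 | 0.96-0.97 | 1.07-1.08 |
| 0.5 | 0.91-0.95 | 1.03-1.04 |
| 0.75 | 0.89-0.92 | 0.99-1.00 |
| 1 | 0.84-0.88 | 0.92-0.96 |

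At p = 0 there is no bias. With a 180-day tail the bias shrinks but remains: 1.10-1.13 is seen as 1.07-1.08 at p = 0.5.

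**6. Effect of stratifying.** The models above are unstratified. I re-ran step 4 with everyone reading 30-35 exposed, in 150,000 sets of one user and five non-users, using a Mantel-Haenszel ratio stratified by set. With sets formed at random, 10% and 50% stopping give 0.92 and 0.66. With sets identical on baseline eGFR they give 0.98 and about 0.91. Matching on a propensity score does not force equal eGFR within a set, so the planned analysis could lie anywhere between.

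**7. Planned analyses that might cover it.** Time-varying exposure reclassifies only time before the first prescription. Fine and Gray models address death. Rosenbaum bounds address unobserved confounders. The adherence groups (MPR) do not alter the censoring rule. None of these follows users past stopping or treats stopping as informative.

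**The case against.** On-treatment follow-up is a conventional choice for drug safety, and the protocol gives a reason for separate safety windows. The large simulated figures need users who started at eGFR 30-35 to be stopped later for being in that same band, although their prescribers had already accepted it. Without that, the first model leaves almost nothing. Weighted and initiation-based sensitivity analyses are also often left to an SAP, which is not shown.

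The argument on size stands. A reader might infer that 10% threshold stopping is enough to cancel the HR 1.10 target. That holds only under the most exposed assumptions; the second model needs p of about 0.75. A reader might also infer that renal harm is certainly hidden, or that users are always removed just before the event. The documents give no stopping rate by eGFR, and a stage 3B user stopped on a reading below 30 has already been counted.

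Nor would it be right to say that no planned analysis could show a sign. The secondary eGFR-change analysis includes the low readings that prompt stopping, and faster decline in users beside a null Cox result would be a partial signal. It would not correct the Cox estimate.

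The appeal to convention does not remove the point. The protocol itself fixes the censoring rule, and its stated reason concerns the onset of adverse events, not the end of follow-up for a gradual outcome found at intermittent tests.

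**Conclusion.** The WP1 rule censors users only, at a decision that can depend on the variable defining the outcome. The censoring is plausibly informative, and threshold-driven stopping of this kind moves the HR towards no renal harm. The size is unknown. Under no drug effect it runs from about 0.98-0.99 to about 0.91 at 10% and 0.65 at 50% stopping, depending on which users are exposed to threshold stopping; tight balance on baseline eGFR within sets would shrink the upper end. These figures rest on assumed stopping rates, test spacing and eGFR slopes, and on a stage boundary of 30. The documents support a caution on interpreting a null WP1 result and a cheap added analysis. They do not support a claim that harm will be missed. No view is taken on when treatment should be stopped.

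**What to change.** Keep the on-treatment analysis and add two analyses for WP1:

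- (a) The same analysis with inverse-probability-of-censoring weights, modelling users' stopping on the latest recorded eGFR. It relies on the readings that prompt stopping being recorded.
- (b) An initiation-based analysis in which users stay in the user group and are not censored at stopping.

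Report both beside the main result, with the secondary eGFR-change analysis, when interpreting a finding of no excess progression. State also when follow-up ends for matched non-users.

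The cost is some extra analysis on prescription and eGFR data that the study already needs. The estimate in (b) is diluted by patients who stop early, which also leans towards no harm, so it should be read with (a) and not in its place.
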